13.10 Finance

This is a clinician-initiated and clinician-led trial funded by Erytech Pharma and Orphan Europe. Pr. [name] [name] is the sponsor on behalf of NOPHO. Erytech Pharma and Orphan Europe will fund the trial with 1.840.000 Euro.

No individual per patient payment will be made to healthcare providers, Investigators or patients.

14.0 ADMINISTRATIVE, ETHICAL, REGULATORY CONSIDERATIONS

The trial will be performed in accordance with the recommendations guiding physicians in biomedical research involving human subjects, adopted by the 18th World Medical Association General Assembly, Helsinki, Finland, June 1964, amended at the 48th World Medical Association General Assembly, Somerset West, Republic of South Africa, October 1996.

The trial will be conducted in accordance with the relevant legislation in the nation state and the International Conference on Harmonisation Guidelines for Good Clinical Practice (ICH GCP).

Before any patients are enrolled into the trial, the Principal Investigator at each site is required to obtain all applicable regulatory approval(s). Sites will not be permitted to enroll patients until written confirmation of such approval(s) have been received by the National Co-ordinating Centre/Sponsor.

It is the responsibility of the Principal Investigator to ensure that all subsequent amendments gain the necessary local approval. This does not affect the individual clinicians' responsibility to take immediate action if thought necessary to protect the health and interest of individual patients.

14.1 Protocol Amendments

Any amendment to the protocol will be written by the Sponsor. Protocol amendments cannot be implemented without prior written IEC approval and Competent Authority approval except as necessary to eliminate immediate safety hazards to patients. A protocol amendment intended to eliminate an apparent immediate hazard to patients may be implemented immediately, provided the IECs are notified within five working days.

14.2 Independent Ethics Committees

The protocol and consent form will be reviewed and approved by the IEC of each participating center prior to study initiation. Serious adverse events regardless of causality will be reported to the IEC in

accordance with the standard operating procedures and policies of the IEC, and the Investigator will keep the IEC informed as to the progress of the study. The Investigator will obtain assurance of IEC compliance with regulations.

Any documents that the IEC may need to fulfill its responsibilities (such as protocol, protocol amendments, Investigator's Brochure, consent forms, information concerning patient recruitment, payment or compensation procedures, or other pertinent information) will be submitted to the IEC. The IECs written unconditional approval of the study protocol and the informed consent form will be in the possession of the Investigator before the study is initiated. The IECs unconditional approval statement will be transmitted by the Investigator to the Sponsor or designee prior to the shipment of study supplies to the site. This approval must refer to the study by exact protocol title and number and should identify the documents reviewed and the date of review.

The IEC must be informed of revisions to other documents originally submitted for review; serious and/or unexpected adverse events occurring during the study in accordance with the standard operating procedures and policies of the IEC; new information that may affect adversely the safety of the patients of the conduct of the study; an annual update and/or request for re-approval; and when the study has been completed.

14.3 Informed Consent Form

Informed consent will be obtained in accordance with the Declaration of Helsinki, ICH GCP, EU Data Protection Directive 95/46/EC and local regulations.

The Investigator will send an IEC-approved copy of the Informed Consent Form to the Sponsor (or designee) for the study file.

A properly executed, written, informed consent will be obtained from each subject prior to entering the subject into the trial. Information should be given in both oral and written form and subjects (or their legal representatives) must be given ample opportunity to inquire about details of the study. If appropriate and required by the local IEC, assent from the subject will also be obtained. If a subject is unable to sign the informed consent form (ICF) a legal representative may sign for the subject. A copy of the signed consent form (and assent) will be given to the subject or legal representative of the subject and the original will be maintained with the subject's records.

It is the responsibility of the Investigator or individuals delegated this responsibility on the delegation of authority log by the Investigator, to obtain written informed consent from the patient or an approved guardian prior to performing any trial related procedure.

Parent/guardian and age-specific Patient Information Sheets are provided to facilitate this process, these documents are prepared in accordance with the national guidelines. Investigators must ensure that they adequately explain the aim, trial treatment, anticipated benefits and potential hazards of taking part in the trial to the patient. The Investigator will also stress that the patient is completely free to refuse to take part or withdraw from the trial at any time. The parent/approved guardian and /or patient should be given ample time (e.g. 24 hours) to read the Information Sheet and to discuss their participation with others outside of the site research team. They must be given an opportunity to ask

questions which should be answered to their satisfaction. The right of the parent/approved guardian and/or patient to refuse to participate in the trial without giving a reason must be respected.

If the parent/approved guardian and/or patient expresses an interest in the patient participating in the trial they will be asked to sign and date the latest version of the Informed Consent Form. The Investigator or designate must then sign and date the form. A copy of the Informed Consent Form should be given to the parent/approved guardian and/or patient, a copy should be filed in the hospital notes, and the original placed in the Investigator Site File (ISF). Once the patient is entered into the trial the patient's trial number should be entered on the Informed Consent Form maintained in the ISF.

It should be recorded in the patient's medicinal records that the patient and/or the parents are informed about the study and have signed the ICF.

Throughout the trial the parent/approved guardian and/or patient should have the opportunity to ask questions about the trial and any new information that may be relevant to the patient's continued participation should be shared with them in a timely manner. On occasion, it may be necessary to re-consent the patient in which case the process above should be followed and the patient's right to withdraw from the trial respected.

Details of all patients approached about the trial should be recorded on the Patient Screening/Enrolment Log. The investigator should obtain the consent of the patient and notify/inform their General/Medical Practitioner that they are taking part in the trial. A Letter to their General/Medical Practitioner should be provided for this purpose.

14.4 Insurance and Indemnity

Patients will be covered by the hospital's insurance in accordance with requirements of the law in the different countries.

14.5 Publication Policy

Results of this trial will be submitted for publication in a peer reviewed journal. The results will be published regardless of being positive, negative or inconclusive. The manuscript will be prepared by the Trial Management Group (PhD student [name] and Sponsor/PI [name] on behalf of NOPHO), Orphan Europe and Erytech Pharma. Authorship will be determined by mutual agreement.

Any secondary publications and presentations prepared by Investigators must be reviewed by the TMG. Manuscripts must be submitted to the TMG in a timely fashion and in advance of being submitted for publication, to allow time for review and resolution of any outstanding issues. Authors must acknowledge that the trial was performed with the support of Erytech Pharma and Orphan Europe Intellectual property rights will be addressed in the "Clinical Study Site Agreement" between Sponsor and site.

There will not be published information that can identify the individual patients.

I have discussed any questions I have regarding the contents of this document with the biostatistical author.

I also understand that any subsequent changes to the planned statistical analyses, as described herein, may have a regulatory impact and/or result in timeline adjustments. All changes to the planned analyses will be described in the clinical study report (CSR).

[figure not shown]
Sponsor Signatory:

[name] [name]

[name]

[name]

Denmark

—DocuSigned by:
Signature: 

Date: 5/18/2021

Sponsor:	NOPHO – Nordic Society of Pediatric Hematology & Oncology		
Protocol:	NOR-GRASPALL 2016		
Document Version No.:	2.0	Document Date:	14-May-2021

History of revision

Version	Changes from the last version
Version 1.0	Original version
Version 2.0	
Due to non-availability of data the following planned analysis has been deleted: Physical Exams, measurement of Vital Signs, performance status, efficacy exploratory analysis, and Correlating Blood Urea Nitrogen levels (BUN) at D14 with Cmax and AUC at steady state
 
Age group has been revised to Children <18 years old and Adult \geq 18 years old
 
One more subgroup analysis added for Children <18: <11 years old and 11-<18 years old
 
Summary Statistics of Antibody titre correlated with Cmax and AUC of eryapsase, has been deleted
 
Section 6.3.1 and 6.4 has been updated

Sponsor:	NOPHO – Nordic Society of Pediatric Hematology & Oncology		
Protocol:	NOR-GRASPALL 2016		
Document Version No.:	2.0	Document Date:	14-May-2021

TABLE OF CONTENT

1. INTRODUCTION AND OBJECTIVES OF ANALYSIS	11
1.1. INTRODUCTION.....	11
2. STUDY OBJECTIVES.....	12
2.1. PRIMARY OBJECTIVE	12
2.2. SECONDARY OBJECTIVES	12
2.3. PRIMARY ENDPOINT	12
2.4. SECONDARY ENDPOINTS.....	12
2.4.1. Pharmacokinetic Evaluation:	12
2.4.2. Pharmacodynamic Evaluation:	13
2.4.3. Immunogenicity:	13
2.4.4. Safety and Tolerability:	13
2.5. EXPLORATORY ENDPOINTS.....	13
3. STUDY DESIGN	14
3.1. SYNOPSIS OF STUDY DESIGN	14
3.2. RANDOMIZATION METHODOLOGY	17
3.3. STOPPING RULES AND UNBLINDING.....	17
3.4. STUDY PROCEDURES	18
4. GENERAL STATISTICAL CONSIDERATIONS AND DATA HANDLING.....	22
4.1. SAMPLE SIZE JUSTIFICATION	22
4.2. GENERAL METHODS	23
4.3. COMPUTING ENVIRONMENT	24
4.4. METHODS OF POOLING DATA	24
4.5. PHARMACOKINETIC, PHARMACODYNAMICS, EFFICACY AND SAFETY VARIABLES.....	24
4.5.1. Pharmacokinetic, Pharmacodynamic, and Immunogenicity Variables.....	24

Table 2	Convention for Imputation.....	27
Table 3	Pharmacokinetic Parameters for Analysis	33

LIST OF IN-TEXT FIGURES

Figure 1	Study Diagram – Patients Treated According to NOPHO ALL 2008	15
Figure 2	Study Diagram – Patients Treated According to NOPHO ALLTogether.....	16

Sponsor:	NOPHO – Nordic Society of Pediatric Hematology & Oncology		
Protocol:	NOR-GRASPALL 2016		
Document Version No.:	2.0	Document Date:	14-May-2021

ABBREVIATIONS

Abbreviation	Definition
AE	Adverse Event
ALL	Acute Lymphoblastic Leukemia
ALP	Alkaline phosphatase
ALT	Alanine Aminotransferase
ASN	Asparagine
ASNase	Asparaginase
ASP	Aspartate
AST	Aspartate Aminotransferase
ATIII	Antithrombin III
ATC	Anatomic Therapeutic Class
AUC	Area Under the Curve
BLQ	Below the limit of quantification
CBC	Complete blood count
CDER	The Center for Drug Evaluation and Research
CL	Clearance
eCRF	Electronic Case Report Form
CSF	Cerebrospinal Fluid
CSR	Clinical Study Report
DI	Dose Intensification
FDA	Food and Drug Administration
EFS	Event free survival

Sponsor:	NOPHO – Nordic Society of Pediatric Hematology & Oncology		
Protocol:	NOR-GRASPALL 2016		
Document Version No.:	2.0	Document Date:	14-May-2021

Abbreviation	Definition
EP	Evaluable patients
GCP	Good Clinical Practice
GLN	Glutamine
GLU	Glutamate
IB	Investigator's Brochure
ICF	Informed Consent Form
ICH	International Conference on Harmonisation
IEC	Independent Ethics Committee
IMP	Investigational Medicinal Product
IV	Intravenous
ISF	Investigator Site File
LDH	Lactate Dehydrogenase
MedDRA	Medical Dictionary for Regulatory Activities
MeMP	Methylated metabolites
MRT	Mean Residence Time
MTX	Methotrexate
NC	Non-calculable
NOPHO	Nordic Society of Paediatric Hematology & Oncology
NS	No Sample
PD	Pharmacodynamic
PI	Principal Investigator
PK	Pharmacokinetic
PP	Per Protocol population

Sponsor:	NOPHO – Nordic Society of Pediatric Hematology & Oncology		
Protocol:	NOR-GRASPALL 2016		
Document Version No.:	2.0	Document Date:	14-May-2021

Abbreviation	Definition
PS	Performance status
PT	Preferred Term
PTT	Partial thromboplastin time
RBCs	Red blood cells
RFS	Relapse free survival
SAE	Serious Adverse Event
SAP	Statistical Analysis Plan
SOC	System Organ Class
TEAE	Treatment-emergent adverse events
6TGN	6 Thioguanine nucleotides
Vss	Distribution Volume at steady state
WHO	World Health Organization

Sponsor:	NOPHO – Nordic Society of Pediatric Hematology & Oncology		
Protocol:	NOR-GRASPALL 2016		
Document Version No.:	2.0	Document Date:	14-May-2021

1. INTRODUCTION AND OBJECTIVES OF ANALYSIS

1.1. Introduction

The Statistical Analysis Plan (SAP) details the statistical methodology to be used in analyzing study data and outlines the statistical programming specifications, tables, figures and listings. It describes the planned analyses of the data collected during the study, including the safety and efficacy variables and populations, anticipated data transformations and manipulations, and other details of the analyses not provided in the study protocol, for the purpose of submission to the relevant authorities and for publication as appropriate. The results of all analyses in this SAP will be included in the Clinical Study Report (CSR).

This SAP is based on the following study documents:

- Protocol Amendment Version 1.0 dated 5th August 2019
- Electronic Case Report Form (eCRF) for the study.

The statistical analyses will be performed in accordance with International Conference on Harmonisation (ICH) E9 guidelines. This SAP conforms to the Cytel standard operating procedure STAT C002 Timing and Content of Statistical Analysis Plans using SAP template STAT C002 TP01 Version 2, dated 19FEB2016.

The SAP should be validated and signed before study database extract for final statistical analysis.

Specifications of outputs (TLFs shells) will be described in a separate document.

Sponsor:	NOPHO – Nordic Society of Pediatric Hematology & Oncology		
Protocol:	NOR-GRASPALL 2016		
Document Version No.:	2.0	Document Date:	14-May-2021

2. STUDY OBJECTIVES

2.1. Primary Objective

The primary objective of this study is to evaluate the pharmacological profile of eryaspase administered to patients with acute lymphoblastic leukemia (ALL) who experience a PEG-asparaginase hypersensitivity event during induction, consolidation or subsequent phases of the multi-agent chemotherapy according to NOPHO ALL 2008 or ALLTogether pilot protocol for the treatment of children and adult patients with ALL. As indicated in the protocol, the pharmacological profile is determined by:

- The pharmacokinetic (PK) parameters for asparaginase activity will be assessed: Cmax; Ctrough (nadir); Tmax; AUC (Area Under the Curve); T1/2 (half-life); Vss (Distribution Volume at Steady State), MRT (Mean Residence Time) and CL (Clearance).
- The pharmacodynamic (PD) parameters for cerebrospinal fluid (CSF) concentrations of asparagine, aspartate, glutamine, and glutamate will be assessed.

2.2. Secondary Objectives

The secondary objectives of this study will further evaluate the eryaspase PK profile, as well as the pharmacodynamic (PD) profile, immunogenicity, safety, tolerability, and metabolites.

2.3. Primary Endpoint

The primary endpoint is the percentage of patients with asparaginase (ASNase) activity >100 U/L at 14 days following the *first* infusion (nadir).

2.4. Secondary Endpoints

2.4.1. Pharmacokinetic Evaluation:

2.4.1.1. Key Secondary Endpoint:

- The percentage of patients with ASNase activity >100 U/L at 14 days following the *fourth* infusion of the 2-week dosing intervals.

Sponsor:	NOPHO – Nordic Society of Pediatric Hematology & Oncology		
Protocol:	NOR-GRASPALL 2016		
Document Version No.:	2.0	Document Date:	14-May-2021

2.4.2. Pharmacodynamic Evaluation:

- Cerebrospinal fluid (CSF) concentrations of asparagine (ASN), aspartate (ASP), glutamine (GLN), and glutamate (GLU)

2.4.3. Immunogenicity:

- Anti-asparaginase antibodies.

2.4.4. Safety and Tolerability:

- Incidence of hypersensitivity (allergic reactions and silent inactivation);
- Adverse events from start of treatment until 30 days after last administration;
- Levels of cytotoxic methotrexate (MTX polyglutamates) and 6 mercaptopurine metabolites (6 thioguanine nucleotides (6TGN) and methylated metabolites (MeMP)) and of DNA-TGN levels in circulating leukocytes.

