4. GENERAL STATISTICAL CONSIDERATIONS AND DATA HANDLING

4.1. Sample Size Justification

The trial is powered to test the hypothesis that 70% of patients meet the >100 U/L threshold compared to the null hypothesis that this threshold is achieved in 50% of patients. The null and alternative hypotheses stated here align with those outlined in previous FDA approvals, such as CDER Application (125359Orig1s000) for Erwinaze in the treatment of ALL. Based on a one-sided significance level of 2.5%, a total of 49 patients will provide 80% power for this comparison in an exact binomial test. A total of 55 patients will be recruited to allow for a ~10% dropout rate for an analysis based on evaluable patients.

Originally, the study was planned for 30 patients. An interim analysis was conducted after first 18 patients enrolled into the study, and study continued to enroll all 35 patients. The protocol was amended in August 2019 to increase the sample size up to 55 patients. The sample size increase was prompted by:

1. Continuous Erwinaze shortage and the need to complete the intended courses of asparaginase therapy
2. Encouraging safety and efficacy profile based on the informal interim analysis in the first 18 patients
3. Note that the sample size increase was not based on any evaluation of the primary endpoint from the study data collected up to that point

The primary population for analysis will be the Evaluable Patient population defined as all patients recruited into the study who provide data on whole blood ASNase activity on Day 14 (+/- 2 days) following the first administration of eryaspase.

A formal statistical hypothesis test will be performed on the primary endpoint. A single sample binomial test will be used to test the null hypothesis at the 2.5% one-sided significance level. The key secondary endpoint with the threshold of 100 U/L following the fourth infusion will be evaluated in the same way. Multiplicity will be controlled across the primary and key secondary endpoint through a pre-specified hierarchy with the primary endpoint in position 1 and the key secondary endpoint in position 2.

Descriptive statistics will be presented. For binary endpoints, 95% confidence intervals for the observed proportions will be calculated using Wilson Score method.

Sponsor:	NOPHO – Nordic Society of Pediatric Hematology & Oncology		
Protocol:	NOR-GRASPALL 2016		
Document Version No.:	2.0	Document Date:	14-May-2021

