4.6.1. Evaluable Patients (EP) Population

This is the primary population for the analysis of the primary and key secondary endpoint(s), defined as all patients recruited into the study who provide data on asparaginase level on Day 14 (+/- 2 days) following the first administration of eryaspase.

The evaluation of the secondary endpoints will also be based on this population but without any imputation for missing data.

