4.6.4. Pharmacokinetic Population

The Pharmacokinetic Population will consist of all patients with an evaluable maximum concentration (Cmax), area under the curve from time 0 to the last measurable concentration (AUC(0-t)), and Ctrough for whole blood ASNase following the first infusion. Analyses of PK data will not use any missing data imputation and will be based solely on observed data.

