4.11.1. Asparaginase Activity and Amino Acids

Missing asparaginase activity data will not be replaced or imputed.

Similar rules will be followed for calculating ASN and GLN levels.

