6.2. Analysis of Key Pharmacokinetic Secondary Endpoints

6.2.1. Pharmacokinetic Parameter Calculations

Pharmacokinetic parameter analyses will be conducted using the Pharmacokinetic Population. The pharmacokinetic parameters to be determined are summarized below, Table 3:

Table 3 **Pharmacokinetic Parameters for Analysis**

Parameter	Description
Cmax	Maximum observed concentration after each administration
tmax	Time corresponding to occurrence of Cmax
Ctrough	Observed concentration at the end of each dosing interval
t1/2	Apparent terminal elimination half-life
AUC(0-t)	AUC from time zero to the last quantifiable concentration
AUC(0-inf)	AUC from time zero extrapolated to infinity following first administration
%AUCex	Percentage of AUC(0-inf) obtained by extrapolation following first administration
MRT	Mean Residence Time
CL	Clearance following first administration
Vss	Volume of distribution following first administration

Sponsor:	NOPHO – Nordic Society of Pediatric Hematology & Oncology		
Protocol:	NOR-GRASPALL 2016		
Document Version No.:	2.0	Document Date:	14-May-2021

PK parameters will be calculated by non-compartmental analysis (NCA) methods from the whole blood concentration-time data using Phoenix WinNonLin version 8.0 and following these guidelines:

- Actual sampling times relative to dosing rather than nominal times will be used in the calculation of all derived PK parameters.
- There will be no imputation of missing concentration data.
- Any subjects with missing concentration data will be included in the PK analysis set provided that at least Cmax and AUC(0-t) can be reliably calculated
- All below the limit of quantification (BLQ) values pre-dose will be substituted by zeros; thereafter, BLQ values between evaluable concentrations will be set to missing
- PK parameters will be estimated according to the following:
 - Cmax and Ctrough will be obtained directly from the concentration-time data.
 - tmax is the time at which Cmax is observed.
 - The terminal phase rate constant (λz) will be estimated by linear regression after log-transformation of the concentrations:
 - Only those data points that are judged to describe the terminal log-linear decline will be used in the regression.
 - A minimum number of three data points in the terminal phase will be used in calculating λz with the line of regression starting at any post-Cmax data point

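### The fourth-infusion key secondary test has no denominator rule of its own. Read as observed-case, it drops patients stopped for no activity, and the stated 80% power does not carry over to it.

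*SAP*

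**What the plan says.** SAP 2.4.1.1 defines the key secondary endpoint as "The percentage of patients with ASNase activity >100 U/L at 14 days following the *fourth* infusion of the 2-week dosing intervals". SAP 4.1 gives one sample size calculation, for 50% against 70% at one-sided 2.5%: "a total of 49 patients will provide 80% power for this comparison in an exact binomial test". It then says "The key secondary endpoint with the threshold of 100 U/L following the fourth infusion will be evaluated in the same way", and places this test second in a hierarchy behind the primary.

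**Population.** SAP 4.6.1 assigns the endpoint to the Evaluable Patients (EP) set, whose only entry condition is a Day 14 (±2 days) level after the first administration. SAP 6.2, headed "Analysis of Key Pharmacokinetic Secondary Endpoints", describes PK parameters and contains no text for this test. Its subsection 6.2.2 ends by basing all analyses on the Pharmacokinetic Population. SAP 4.6.4 defines that set by evaluable Cmax, AUC(0-t) and Ctrough after the first infusion.

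**Missing data.** SAP 4.6.1 says "The evaluation of the secondary endpoints will also be based on this population but without any imputation for missing data". SAP 4.11.1 says "Missing asparaginase activity data will not be replaced or imputed", and SAP 4.6.4 says "Analyses of PK data will not use any missing data imputation and will be based solely on observed data".

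**Who reaches infusion 4.** SAP 3.1 allows 1 to 7 eryaspase doses, depending on how many asparaginase courses remain. Protocol 7.6 discontinues eryaspase for, among other things, clinical allergy of any grade and absence of asparaginase activity. Protocol 11.1 lists lack of activity only among possible reasons for stopping.

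**The concern.** Two kinds of EP patient have no Day 14 value after infusion 4. Some were never scheduled for four 2-week infusions. Others were scheduled but stopped earlier. The SAP states no rule for either kind, and two sections of it point to different populations.

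The second kind matters most. A patient discontinued because activity was absent has failed on exactly what this endpoint measures. Under an observed-case analysis that patient leaves both numerator and denominator, and the remaining patients look better than the group that set out to receive four infusions. This is selection on the outcome, in a test that carries a formal 2.5% level.

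The only n and power in the SAP belong to the first-infusion endpoint. The number with a fourth-infusion trough cannot exceed the number scheduled for one, and the SAP gives neither. A reader cannot tell whether a non-significant second test would reflect low activity or few patients.

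**Working it through.** **Inputs.** Null 0.50, alternative 0.70, one-sided 2.5%, exact binomial test, 49 evaluable, about 10% dropout, 55 recruited (SAP 4.1). Dose range 1 to 7 (SAP 3.1). The n at infusion 4 and the share stopped early are not in the documents and are varied below.

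**1. The plan's own figure.** Let c(n) be the smallest r with P(X ≥ r | n, 0.5) ≤ 0.025. Power is P(X ≥ c(n) | n, 0.7).
- n=49: c=32, exact level 0.022, power 0.810.
- n=48: c=32, power 0.750. n=47: c=31, power 0.780, the highest of any n below 49.
- Recruitment: 49/(1−0.10) = 54.4, rounded up to 55.

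The stated figures reproduce, and no n below 49 reaches 80%.

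**2. The same test at smaller n (assumed values).**

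| n with a fourth trough | c | Power at true 70% |
|---|---|---|
| 49 | 32 | 81% |
| 44 | 29 | 78% |
| 40 | 27 | 70% |
| 35 | 24 | 65% |
| 30 | 21 | 59% |
| 20 | 15 | 42% |

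**3. Why n may be below 49.** Protocol 1.0 describes five PEG-asparaginase doses at 2-week intervals in NOPHO ALL 2008. A patient reacting at dose k has 5−k such doses left, or 6−k if the reacted-to dose is itself replaced. At k=3 that is 2 or 3, never four. At k=2 it is 3 or 4. Protocol 1.0 says 85% of allergic Nordic children reacted after dose 2 or 3, without the split. For ALLTogether, protocol 7.4.2 gives an overall maximum of 3 to 7 doses and then risk-group maxima of 4, 5 and 8. Whether a very-low-risk patient can have a fourth infusion depends on which count applies.

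**4. Size of the observed-case bias.** Let m be the share of scheduled patients removed before the fourth trough and f the share of those removed who are failures. With a true rate of 0.5, the rate among those left is q = (0.5 − m(1−f))/(1−m).
- f=1, m=0.077: 0.5/0.923 = 0.542.
- f=1, m=0.20: 0.5/0.80 = 0.625.
- f=0.75, m=0.20: (0.5−0.05)/0.80 = 0.5625.
- f=0.5: q = 0.5 for any m, so no bias.

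With 30 scheduled, the number removed k ~ Bin(30, m), and the remainder tested at its own critical value, the rejection rate is the sum over k of P(k)·P(X ≥ c(30−k) | 30−k, q).

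| Removed | 30 scheduled, f=1 | 20 left, f=1 | 20 left, f=0.75 | 20 left, f=0.5 |
|---|---|---|---|---|
| 0 | 2.1% | 2.1% | 2.1% | 2.1% |
| 7.7% | 4.1% | 4.8% | – | 2.1% |
| 20% | 17% | 18% | 6.9% | 2.1% |

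If the removed failures are instead counted as failures among all 30, the rate stays at 2.1%. These rates are for the second test taken alone, without the requirement that the primary reject first.

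The 7.7% is the allergic-reaction rate that protocol 2.1.2 reports for non-allergic eryaspase patients in an earlier trial. It serves only as a scale, since that trial had no withdrawals for hypersensitivity. The 20% is assumed.

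**5. Illustration (assumed data).** Thirty patients are scheduled for four infusions, 4 are stopped for no activity, and 20 of 26 troughs exceed 100 U/L.
- Observed-case: 20/26 = 77%, one-sided p = 0.005, rejects.
- No-activity stops counted as failures: 20/30 = 67%, p = 0.049, does not reject at 2.5%.

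**The case against.** **The SAP is not silent.** It bars imputation in several places, and the endpoint's wording presupposes a fourth infusion, so observed-case is what an analyst would most likely do. That is right, and it narrows the ambiguity. It does not remove the problem, because observed-case is the reading that drops the failures.

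**A reader might go further** and infer that all 49 EP patients form the denominator, with everyone lacking a fourth trough counted as a non-success. Then 32 successes would be needed; power at a true 70% would be 42% if 44 patients reach infusion 4, and rejection would be impossible if fewer than 32 do. The documents support this reading only weakly. It would assign an outcome to patients never due the infusion, against the no-imputation wording.

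**The bias figures are a worst case.** This stands. They assume that every removed patient is a failure, and the bias vanishes if removed patients fail at the same rate as the rest. In particular, a reader might want every allergy stop counted as a failure in the main analysis. Protocol 7.6 stops for allergy of any grade whatever the activity, so that is a debatable choice of estimand and belongs in a sensitivity analysis.

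**Power for a secondary endpoint is optional, and other outputs help.** The SAP plans Wilson intervals, a per-protocol sensitivity analysis, discontinuations by reason and by-subject listings. These let a reader see n and precision. They do not correct the selection: the per-protocol set is drawn from the same EP set and has no rule for early stops. The hierarchy also limits when the second test is formal, and SAP 4.8 sits awkwardly with SAP 4.1 by saying that multiplicity is not a concern.

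**The PK parameter summaries might be thought free of the gap** because they have their own population. They are not, since that population too is fixed at infusion 1. They are descriptive, however, and no test depends on them.

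**Conclusion.** The concern holds and should be fixed before fourth-infusion results are analysed. The formal second test has two candidate populations, both defined at infusion 1, and no rule for patients stopped before the fourth trough. Observed-case analysis, the natural reading though an inference, removes patients stopped for no activity and biases the percentage upward.

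The size depends on quantities that the documents do not give. With 30 scheduled and a true 50%, the worst case takes one-sided rejection from 2.1% to 4.1% or 17%, at assumed removal shares of 7.7% and 20%. It is smaller when only some removed patients are failures: 6.9% rather than 18% with 20 left, 20% removed and three quarters of them failures. None of these is a forecast.

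The 80% power figure requires 49 evaluable patients and applies to the primary endpoint only. A reader might infer from the timing of PEG-asparaginase reactions that very few patients will have a fourth 2-week infusion. The documents do not establish that: the split between dose 2 and dose 3, the mix of treatment protocols and replacement of the reacted-to dose are not stated. The primary endpoint is not affected.

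**What to change.** In SAP 2.4.1.1, 4.1, 4.6.1 and 6.2:
1. Name one population for this endpoint and resolve EP against the Pharmacokinetic Population.
2. Define the denominator as EP patients whose treatment schedule included at least four 2-week eryaspase infusions. For ALLTogether, take the schedule after risk stratification, because patients may switch in induction, before the day 29 stratification.
3. Count a stop before the fourth trough for no asparaginase activity as not above 100 U/L. State in SAP 4.11 and 4.11.1 that this is an outcome rule and not imputation.
4. Report two sensitivity analyses: (a) allergy stops also counted as failures; (b) observed cases only.
5. Tabulate other missing fourth troughs by reason, and give no asparaginase activity its own category in SAP 5.1, where it now falls under others.
6. State that 80% power applies to the primary endpoint only, and report the fourth-infusion n with its exact power.

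Apply the same rule to the fourth-infusion percentages in SAP 2.5 and 6.2.3. Record the change and its reason in SAP 9, since PK was already reviewed in the first 18 patients (SAP 4.13). Protocol 7.6 and 11.1 on lack of activity, and the dose counts within protocol 7.4.2, must be reconciled.

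**Cost.** No new samples. The work is SAP wording, a count of scheduled 2-week infusions per patient (SAP 7.3 already needs total infusions planned), and a stop reason that protocol 11.1 already requires in the CRF. The price is a slightly lower fourth-infusion estimate and a little more analysis.
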